Within the division/department, what Center or group are you affiliated with, if any?
Depression Evaluation Service

Unaffiliated Personnel

List investigators, if any, who will be participating in this protocol but are not affiliated with New York State Psychiatric Institute or Columbia University. Provide: Full Name, Degrees and Affiliation.
None

Procedures

To create the protocol summary form, first indicate if this research will include any of the following procedures

- ✓ Psychiatric Assessment
- ✓ Use of Placebo or Sham Treatment
- ✓ Medication-Free Period or Treatment Washout
- ✓ Somatic Treatment or Intervention
- ✓ Internet-based Data Collection or Transmission

Population

Indicate which of the following populations will be included in this research

- ✓ Adults
- ✓ Adults over 50
- ✓ Employees or Students
- ✓ Individuals with HIV/AIDS

Research Support/Funding

Will an existing internal account be used to support the project?

Yes

Describe internal account

Any DES account from which project expenses can be drawn (specifically, **light boxes, activity monitors, amber and clear goggles**, and melatonin collection/analysis costs)

Is the project externally funded or is external funding planned?

No

Study Location

Indicate if the research is/will be conducted at any of the following

- ✓ NYSPI
- ✓ Other Columbia University Medical Center Facilities

This protocol describes research conducted by the PI at other facilities/locations

Yes

- ✓ Other Facilities

Other Facilities

Type in location(s)

[name]

Lay Summary of Proposed Research

Lay Summary of Proposed Research

Research Question: Is Chronotherapy (i.e., missing a night of sleep, shifting sleep time and bright morning lights to adjust the biological clock) effective treatment for non-bipolar depression?

Antidepressant medications do not result in quick remissions and they produce side effects. "Jet lag" can be thought of as resulting from the internal clock being out of sync with external time; as the internal clock aligns with sun time, the symptoms of jet lag lessen. Preliminary data suggest some depressed patients act as if their internal biological clock is out of sync with the outside world and re-aligning their clock with the timing of sunlight lessens their depressed mood and accompanying depressive symptoms. This "chronotherapy" may produce remission during the first week of treatment while causing minimal problems. This study aims to demonstrate the efficacy of chronotherapy by comparing its efficacy to an alternative protocol we consider unlikely to produce the same effects. Whether a given patient will be instructed to use chronotherapy or the alternative protocol will be determined randomly (i.e., by chance, essentially a computerized flip of a coin). Prior to determination of which protocol a patient will follow, each patient will declare their desired sleep time (for example, 11 p.m. to 7 a.m.). All patients will be assigned specific times to sleep and sit in front of bright lights wearing clear (Chronotherapy) or amber (alternative protocol) goggles. Those assigned Chronotherapy will miss a night of sleep while those in the alternative protocol will not; assigned sleep times will also differ between groups using different strategies to shift the timing of their sleep from their ideal sleep time as determined by their MEQ score to their desired sleep time. All subjects will be rated daily by telephone for the first week after their Wake Night (those assigned Chronotherapy) or for the first week following randomization (those assigned the alternative protocol), and then weekly for an additional five weeks. Whenever possible, weekly visits will be in person, although telephone visits will be allowed. All subjects will be rated at baseline, 1 week and 6 weeks by an Independent Evaluator blind to treatment assignment. After the six week post-randomization evaluation, all subjects will be offered six months of continued treatment and be rated monthly. Treatment during this six month period may consist of Chronotherapy or conventional antidepressants as the patient and doctor determine. Standard ratings of depression, over-all illness and functioning will be obtained; melatonin, sleep logs and activity monitoring will measure the timing of the biological clock. Change in the symptom measures will determine whether chronotherapy is as effective as, less effective than or more effective than the alternative treatment. Chronotherapy will be judged effective if it is more effective than the alternative treatment. Secondary analyses will analyze timing of melatonin rise, timing of sleep and activity to determine whether the timing of the biological clock changes, and if so whether clock changes correlate with improvement. Measures of functioning will determine whether functioning improves coincident with, independent of or subsequent to mood improvement.

Background, Significance and Rationale

Background, Significance and Rationale

While chronotherapy (variously including some number of nights without sleep coupled with early morning bright lights and set times for sleep with or without an advance in the timing of allowed sleep) has some degree of acceptance as effective treatment for affective disorders, the majority of the literature addresses bipolar illness. We found three studies that address depressed patients who do not have bipolar disorder. One concluded that chronotherapy is more effective for and is more quickly effective in depressed patients with bipolar disorder than those without a bipolar history, but conclusions as to whether this treatment is effective for nonbipolar patients cannot be made as there was no comparison condition (Barbini, 1998). Two studies (Martiny, 2012; Sahlem, 2014) included nonbipolar depressed subjects but neither separately reported response by polarity, although one stated that the nonbipolar subjects' response "did not differ". Both, however, also gave patients standard antidepressant treatment; i.e., chronotherapy was used as an add-on or augmentation rather than as the only treatment. Thus, Chronotherapy for nonbipolar depression appears to us to be insufficiently studied to judge its efficacy in this population. Our preliminary work (IRB #5491 and #6938) suggest our version of chonotherapy may be effective alone for nonbipolar depression. To date, we have treated 18 such patients; 10 (56%) were remitted at 1 week and 10 (56%) were remitted at 6 weeks. These results compare favorably to antidepressant medications. Szegedi (see uploads), for example, compiled data from 41 randomized, controlled trials; no drug resulted in increased remissions at week one relative to placebo. Rapidly titrated mirtazapine resulted in significantly more remissions than placebo at week 2 (13% vs 7%), while all other drugs including usual dose mirtazapine, venlafaxine, selective serotonin re-uptake inhibitors, tricyclic antidepressants, trazodone and matprotyline separated from placebo at week 3 or later. Even at week 6, the highest remission rate was TCA at 40%. So, even considering the 95% confidence limits of 10 out of 18 range from 31-78%, these two open pilot studies raise the possibility that some patients can improve quickly, even in days, rather than the weeks it takes antidepressant medications to produce remissions. Definitive studies demonstrating the ability of chronotherapy to produce rapid remissions have not been conducted. This study aims to fill that void.

Specific Aims and Hypotheses

Specific Aims and Hypotheses

Research Question

Is Chronotherapy effective treatment for nonbipolar depression?

Specific Aim #1: Demonstrate that Chronotherapy is effective treatment for nonbipolar depressive illness after one week of treatment.

Specific Aim #2: Demonstrate that Chronotherapy is effective treatment for nonbipolar depressive illness after six weeks.

Specific Aim #3: Demonstrate that Chronotherapy shifts the biological clock.

Hypothesis #1: Patients assigned Chronotherapy will be more likely to be remitted at week 1 than those assigned alternative treatment.

Hypothesis #2: Patients assigned Chronotherapy will be more likely to be remitted at week 6 than those assigned alternative treatment.

Hypothesis #3: Shift (earlier) of the onset of night-time melatonin secretion levels will be greater in chonotherapy-treated patients than in those receiving alternative treatment.

Description of Subject Population

Sample #1

Specify subject population

nonbipolar depression

Number of completers required to accomplish study aims

60

Projected number of subjects who will be enrolled to obtain required number of completers

75

Age range of subject population

18-65

Gender, Racial and Ethnic Breakdown

We anticipate our study population will consist of roughly:

Females 60%

Hispanics 15%

Race

Caucasian 65%

African-American/Black 15%

Asian 15%

Other/Mixed/Unstated 5%

Description of subject population

As above

Recruitment Procedures

Describe settings where recruitment will occur

Depression Evaluation Service: 3rd Floor New York State Psychiatric Institute, [name]

[name]: [name]

How and by whom will subjects be approached and/or recruited?

We anticipate that most patients will be approached and recruited by the clinician interviewing patients in IRB Protocol #6669R once it has been presumptively determined that all inclusion and no exclusion criteria have been met.

Additional patients initially recruited for another DES study may be suggested for this study once they complete any treatment portion of the other study (patients in the post-treatment follow-up phase of the other study will be eligible for recruitment into this protocol assuming they meet all inclusion and no exclusion criteria, agree to and sign consent for this protocol). Such patients from other protocols will either be recruited by their clinician in the other study (if that clinician is authorized to obtain consent for this protocol) or referred by the other study's clinician to a DES clinician authorized to obtain informed consent for this protocol.

Patients referred from other NYSPI clinicians and from CUMC will be interviewed and recruited through Protocol #6669R.

How will the study be advertised/publicized?

We do not envision advertising this study at this time. However, should we decide to advertise, any text and/or pictures will be submitted to the IRB for approval prior to their use, which will occur only after IRB approval. Non-advertising publicity may occur from time to time in the form of publicized interviews such as appearances on talk shows or news reports and print media articles based on interviews.

Do you have ads/recruitment material requiring review at this time?

No

Does this study involve a clinical trial?

Yes

YOU MUST REGISTER AT [ClinicalTrials.gov](https://clinicaltrials.gov) IMMEDIATELY UPON RECEIPT OF IRB APPROVAL AND **PRIOR TO ENROLLMENT OF THE FIRST SUBJECT. YOU WILL BE PROVIDED WITH A NCT REGISTRATION NUMBER ON REGISTRATION. PLEASE REVISE THIS SECTION OF THE PROTOCOL SUMMARY FORM TO INCLUDE THE NCT NUMBER AND RE-SUBMIT AS AN AMENDMENT TO THE IRB.**

Concurrent Research Studies

Will subjects in this study participate in or be recruited from other studies?

Yes

Describe concurrent research involvement

Protocol #7088 involves a single blood draw to analyze for epigenetic markers; this blood draw may occur while patients participate in this protocol

Protocol #6669R is the DES Screening Protocol which most patients entering this study will complete prior to entry to this protocol

Protocol #5768 is a study of Cognitive Behavior Therapy; patients who do not remit upon completion of that protocol may be offered participation in this protocol, while non-remitters in this protocol may be offered treatment in #5768

We are still following some participants in Study #6457 (which compared desvenlafaxine to placebo) and #6263 (AKA #7160R) (which compared sertraline to placebo, non-responders crossed to bupropion or sertraline, respectively). While unlikely, should any such patients be eligible for this study, we would approach them. We would not endeavor to make them eligible, for example, by stopping current treatment in order to produce eligibility.

Inclusion/Exclusion Criteria

Name the subject group/sub sample
nonbipolar depression

Create or insert table to describe the inclusion criteria and methods to ascertain them

- | | |
|---------------------------------------|---|
| 1. Age 18-65 | 1. Ask patient and compare stated age to reported DOB |
| 2. Currently depressed | 2. Has an affective disorder diagnosis per SCID interview (i.e., major depression, persistent depressive disorder, unspecified depressive disorder) |
| 3. In reasonably good physical health | 3. No active medical problem not under good control (e.g., someone with hypertension whose current blood pressure is in the normal range, someone with diabetes having a hemoglobin A1C < 7; abnormal thyroid tests [low TSH in someone taking thyroid medication is OK]; so, medical history (from patient), labs, and when indicated discussion with primary care physician |

Create or insert table to describe the exclusion criteria and methods to ascertain them

- | | |
|--|-------------------|
| 1. Bipolar disorder (I, II or unspecified) | 1. SCID interview |
|--|-------------------|

2. History of psychosis	2. SCID interview
3. Unstable medical condition	3. medical history, labs, physical examination
4. Current (past six months) drug or alcohol use disorder	4. SCID interview; urine toxicology
5. Need for hospitalization	5. Clinician's judgment based on depression severity, suicidality or any other reason
6. Treating clinician determination not to include patient in this protocol	6. Clinician's judgment
7. Currently taking medication approved for the treatment of depression	7. Patient report
8. Un- or poorly controlled hypertension	8. BP on repeated readings of ≥ 150 systolic or ≥ 100 diastolic
9. Pregnancy	9. Patient report; lab test

Waiver of Consent/Authorization

Indicate if you are requesting any of the following consent waivers
 Waiver of consent for use of records that include protected health information (a HIPAA waiver of Authorization)
 No
 Waiver or alteration of consent
 No
 Waiver of documentation of consent
 No
 Waiver of parental consent
 No

Consent Procedures

Is eligibility screening for this study conducted under a different IRB protocol?
 Yes
 Indicate NYSPI IRB #
 6669R
 Describe Study Consent Procedures
 The consenting clinician after determining the patient is presumptively eligible (e.g., prior to lab results

returning) will explain the study procedures as well as alternatives, risks and possible benefits, answer any questions and offer the IRB approved study consent, watch the patient read the consent, answer any further queries and then watch while the patients signs the consent.

Indicate which of the following are employed as a part of screening or main study consent procedures

- ✓ Consent Form
- ✓ Information Sheet

Persons designated to discuss and document consent

Select the names of persons designated to obtain consent/assent

[name]

[name]

Type in the name(s) not found in the above list

Study Procedures

Describe the procedures required for this study

Potential participants will be interviewed under Protocol #6669R. Those meeting all Inclusion Criteria and no Exclusion Criteria will be offered participation in the study. For clarification purposes, no otherwise eligible subject will be offered participation in this study who is currently taking approved antidepressant medication and the DES will not suggest or recommend discontinuation of such medication in order to create an eligible subject. Informed consent will be obtained prior to any procedures specific to this protocol. If labs and physical have been done within three months, these will be obtained and reviewed; potentially exclusionary labs will either exclude the subject or be repeated to determine eligibility vs. exclusion; such recent labs and physical examinations will not be repeated unless the consenting physician deems a repeat appropriate; urine for pregnancy and drug testing will be obtained from all potential subjects whether recent such tests exist or not. All other patients who sign consent will have blood drawn, urine collected, EKG obtained and physical examination performed. Blood analyses will include SMA-25 (which assesses kidney and liver function, several electrolytes such as calcium, sodium and potassium and some other bodily functions), TSH (assessing thyroid function); urinalysis measures kidney and bladder function; other analyses of urine will test for commonly abused substances and pregnancy (if appropriate). Electrocardiogram assesses heart function. The Mini-Mental Status Examination (given to those over 60 years of age) assesses cognitive function (such as memory). Patients and doctors will complete a variety of ratings to assess mood, over-all symptoms, the timing of their biological clock and psychosocial functioning (see Table in "Uploads" for schedule of when ratings are done and by whom, and "Assessment Instruments" below for names, acronyms and descriptions of the assessment scales). Patients will be given an activity monitor to wear and sleep/activity/mood logs to complete daily. They will return in 1-2 weeks (although at patient's discretion, this time will be allowed to last up to 30 days) at which time mood symptoms will be reassessed. Those who do not remain depressed will not receive further treatment through the protocol although they will be offered three months of "open treatment" (i.e, they can consult with a DES psychiatrist who will prescribe whatever treatment the patient and doctor agree upon and available to the DES psychiatrist to use). Those still depressed will be randomly assigned to treatment with Chronotherapy or

alternative treatment (see below for descriptions). Prior to randomization, all patients will declare what time they desire to end up sleeping ("desired sleep time").

Chronotherapy

Patients assigned chronotherapy will determine which night during the ensuing week they will be able to miss a night of sleep ("Wake Night"); their chronotherapy protocol will begin that night. Following their Wake Night, they will be instructed to sleep 8 hours at specific times; their first allowed sleep will be on the evening following their Wake Night starting at six hours prior to their desired sleep onset time. Their second allowed 8 hours of sleep time will be the following night starting three hours prior to their desired sleep onset time. Those whose desired sleep time is within two hours of the times determined by their responses to the Morningness-Eveningness Questionnaire (MEQ) will thereafter be instructed to sleep only at their desired sleep time. Subjects whose desired sleep time is more than two hours earlier than their MEQ derived ideal sleep time will be given instructions to sleep desired minus six and desired minus 3 hours the initial two allowed sleep nights; thereafter their allowed sleep will be later and later in maximal 3 hour increments until allowed sleep coincides with MEQ determined sleep times; thereafter, their allowed sleep will shift half an hour earlier every two-four days (depending on their ability to waken earlier) until their allowed sleep coincides with their desired sleep time. Whichever allowed sleep paradigm is followed, once sleep is at the desired time, their allowed sleep time will remain their desired sleep time thereafter. Patients whose desired sleep time is within two hours of their MEQ-determined ideal sleep time will sit in front of the bright lights wearing clear goggles throughout at their desired wake-up time beginning the morning following their Wake Night. Those whose MEQ-determined ideal sleep time is more than two hours different from their ideal sleep time will initially sit in front of the bright lights at their MEQ-determined ideal wake-up time, also beginning the morning following their Wake Night; as wake-up times shift earlier, time in front of the bright lights will shift with their allowed wake-up time. For the six weeks following randomization, whenever they sit in front of the light box, patients will be instructed to wear clear goggles.

To date, the longest time from wake-up prior to institution of a "Wake Night" until post-Wake Night allowed sleep has been 42 hours. Should time from prior wake-up to six hours earlier than desired sleep onset time project to more than 42 hours, first allowed sleep time will be shifted earlier so that first allowed sleep time is no more than 42 hours after their previous day's wake-up time. An additional day or days of shifting sleep will be added such that three hour per day increments (likely shorter on the last night) in allowed sleep time ends at their desired sleep time.

Should any patient have difficulty getting to sleep at the assigned time and/or waking at the prescribed time, they will enter a remedial protocol. This protocol will allow such patients to go to sleep when they feel tired and spontaneously waken for two nights, using the bright lights at the time they spontaneously waken (or at the previously assigned time if spontaneous wakening is earlier than the assigned time). The mean go to sleep and wake-up times of these two nights will determine their allowed sleep onset and wake-up times and the resulting wake-up time will be their new time to sit in front of the bright lights. They will then shift their allowed sleep and light use times half hour forward or back as appropriate until they are sleeping at their desired time and using the bright lights at their desired wake-up time. Should they have trouble shifting in half-hour decrements, shorter decrements will be used.

Alternative treatment

Patients randomized to alternative treatment will also be assigned specific allowed 8 hour sleep times and sit in front of the bright lights for half an hour each morning. Patients assigned alternative treatment will NOT miss a night of sleep; that is, they will not have a Wake Night. Their allowed sleep times will start at their MEQ-determined ideal sleep time. Subsequently, allowed sleep will shift in half hour increments or decrements as appropriate until allowed sleep coincides with desired sleep. They will sit in front of the bright lights each morning on waking up. Whenever they sit in front of the light box, they will be instructed to wear the amber goggles. The remedial protocol above will be followed with any patient unable to shift their sleep.

Ratings and timing of ratings will be identical for all patients. That is, all will complete the same rating scales throughout. In particular, all subjects will log in for 12 hours out of 24 during their initial 24 hours post-randomization, complete daily mood, sleep and energy logs, wear an activity monitor and have call-in interviews daily during the first post-randomization week. All will be interviewed by an independent evaluator blind to treatment assignment at baseline and Weeks 1 and 6, with ratings by their study clinician daily for the first week and weekly thereafter. At week 6, remitters will be recommended to continue bright light and allowed sleep times, although they will be asked to return their light boxes, goggles and activity monitors. Nonremitters will be offered alternative treatment, including Chronotherapy if assigned to the alternative treatment group and standard antidepressants whichever their assigned study treatment. All randomized subjects will continue to be seen at least monthly for six months with continued ratings each month.

Use of Light Boxes

All fecund women will be instructed to stop using the light box should they become pregnant. Also, regardless of group assignment, patients will be instructed to sit about 18 inches from the light box with eyes open but not looking directly at the light; instead they should read or use their computer or other sedentary activity. They should remain 18 inches from the light for 30 minutes. However, should side effects occur (e.g., overstimulation), the time may be decreased. Tolerance of the light box plus continuing depressed mood will trigger the doctor recommending longer light box use in weekly 15 minute increments up to 60 minutes total; first available increment would be at the week 2 visit, decrements can occur at any time.

Melatonin

All randomized subjects on the night they are randomized will collect saliva to later be analyzed for melatonin. They will be given tubes each of which contains a cotton swab with instructions to place a swab in their mouth every half hour (so, nine swabs = over a four hour period), write the date and time each swab was collected on the tube, refrigerate until they bring the vials in at their next visit. This is repeated over a three hour period at approximately one week (patients who have difficulty reaching their intended sleeping time will delay 2nd saliva collection until they reach their desired sleep time). In order to prevent ambient light from preventing melatonin secretion, all subjects will be issued blue-blocking amber goggles with instructions to wear them from an hour prior to start of saliva collection until the last saliva collection on each of the two nights during which saliva is collected.

Independent Evaluation

All study subjects who are randomized will be evaluated by someone who has no idea what their treatment has been, whether treatment has begun or how long treatment has been if currently being treated. These

Independent Evaluations will occur prior to institution of post-randomization procedures (typically on day of randomization), at the end of Week 1 and at the end of Week 6 post-randomization. If possible, this evaluation will be in person, but when in person interviewing is not possible these evaluations will be made by telephone. Independent Evaluators will be instructed not to ask any questions about treatment or where the interviewee is in the study. Participants will be instructed not to say anything to the Independent Evaluator about whether they are in treatment, or if in treatment what that treatment might be.

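### No written criterion keeps stable, controlled epilepsy or a remote past seizure out of an outpatient Wake Night of about 34 hours followed by 10,000 lux light

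*Protocol*

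**What the plan says.** The eligibility rules are in the Protocol's Inclusion/Exclusion Criteria tables. The SAP does not address them.

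- Inclusion 3 (physical health) requires "No active medical problem not under good control". Its examples admit chronic disease when controlled, such as hypertension with normal current readings or diabetes with an acceptable haemoglobin A1C.
- Exclusion 3 is "Unstable medical condition".
- Exclusion 6 is "Treating clinician determination not to include patient in this protocol", ascertained by judgment, with no grounds listed.
- Exclusion 7 is "Currently taking medication approved for the treatment of depression". Antiepileptic drugs are not named.

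The remaining exclusions are bipolar disorder, past psychosis, recent substance use disorder, need for hospitalization, poorly controlled hypertension and pregnancy.

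Under Study Procedures (Chronotherapy), the patient misses a night of sleep. The first permitted sleep comes the following evening, "starting at six hours prior to their desired sleep onset time", subject to a limit under which "first allowed sleep time is no more than 42 hours after" the previous day's wake-up. Daily morning light follows. The risk section gives its intensity as 10,000 lux. Seizure is not mentioned in the criteria, the screening procedures, the risks or the risk-minimization text.

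**The concern.** Every medical criterion turns on whether a condition is active, uncontrolled or unstable. A recent, unexplained or uncontrolled seizure could be caught that way. Stable epilepsy or a remote seizure could not, because it passes the good-control test even when the history brings it to light. Study Procedures says that patients who meet all inclusion and no exclusion criteria will be offered the study, so enrolment is the default.

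This is a patient-safety matter. The protocol draws its supporting evidence on sleep deprivation from studies that mostly left this group out, so those studies cannot show how the group tolerates a missed night. The setting is also less supervised. The uploaded studies used inpatients, and in one of them nursing staff ensured adherence. Here contact is by log-in and telephone. As worded, "all subjects will log in for 12 hours out of 24 during their initial 24 hours post-randomization", yet the Wake Night may be any night of the week after randomisation, so the log-ins need not even coincide with it.

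**Working it through.** **Step 1: read each criterion against the two cases** (stable controlled epilepsy; one remote seizure).

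- Inclusions 1 and 2 (age, depression): met.
- Inclusion 3: met, since the problem is controlled or no longer active.
- Exclusions 1, 2, 4, 8 and 9: unrelated conditions.
- Exclusion 3: does not apply, because the condition is not unstable.
- Exclusion 5: concerns need for admission, so does not apply.
- Exclusion 7: covers only drugs approved for depression.
- Exclusion 6: could apply, at the clinician's discretion.

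So no inclusion criterion and none of the eight other exclusions stops enrolment; only exclusion 6 could.

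**Step 2: hours awake.** The protocol states the 42-hour limit but no typical figure. Let S be desired sleep onset and W the wake-up time before the Wake Night, both on a 24-hour clock. Then

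hours awake = 24 + (S − 6) − W, capped at 42.

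- Lay Summary example, 11 p.m. to 7 a.m.: 24 + (23 − 6) − 7 = 34.
- Anyone waking at the end of an 8-hour sleep at the desired time has W = S − 16, which gives 24 − 6 + 16 = 34 whatever S is.
- Prior wake-up 3 hours later than desired: 31. Prior wake-up 3 hours earlier: 37.

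**Step 3: the protocol's own uploads, side by side.**

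- Inpatient triple chronotherapy pilot (one night of 33 to 36 hours awake, phase advance, 10,000 lux light): excluded any history of seizures, listed separately from active unstable medical or neurologic illness.
- Inpatient study of unipolar and bipolar response to sleep deprivation: required no history of epilepsy, listed separately from major medical and neurological disorders.
- Inpatient randomised wake therapy trial: excluded light-induced epilepsy. Whether its organic brain disorder exclusion covered other epilepsy is not stated.

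The pilot's regimen is the closest to this one. The second half of its criterion resembles exclusion 3 here, so its authors did not rely on an unstable-illness rule to cover seizure history. The uploaded eye-safety study of bright light also excluded epilepsy, but it is not relied on: its list excludes diabetes too, which this protocol admits when controlled.

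**Step 4: how often such a patient would be exposed.** The documents give no prevalence, so 0.5% to 2% is assumed. The number randomised lies between 60 (the required completers) and 75 (projected enrolment), because not all enrolled patients are randomised: "Those who do not remain depressed will not receive further treatment through the protocol".

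Expected number in the Chronotherapy arm = N × prevalence / 2:

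- N = 60: 60 × 0.005 / 2 = 0.15; 60 × 0.02 / 2 = 0.60.
- N = 75: 75 × 0.005 / 2 = 0.19; 75 × 0.02 / 2 = 0.75.

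Chance of at least one = 1 − (1 − prevalence)^n:

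- n = 30: 1 − 0.995^30 = 0.140; 1 − 0.98^30 = 0.455.
- n = 37: 1 − 0.995^37 = 0.169; 1 − 0.98^37 = 0.527.

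These figures assume that exclusion 6 is never used. They measure exposure, not injury.

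**The case against.** The strongest reply is that the documents show no risk. None says that one missed night, or 10,000 lux, provokes seizures in stable patients, and the precedents give no reason for their exclusions. Those studies differ in other ways: two planned three wake nights, the pilot's patients were all on antidepressants, and their lists contain items nobody proposes to add here, such as panic disorder or glaucoma. The uploaded review of chronotherapeutics describes sleep deprivation across a wide range of depressed patients without an evident seizure caution. The history would probably disclose the condition, and the clinician may then decline. Screening runs under a separate protocol (#6669R), which was not supplied, and the consent pages are not available, so a seizure question or warning may exist there. The prevalence is assumed.

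Much of this stands as a limit on weight. The harm cannot be sized, and the probabilities are only illustrative. It does not change what the written criteria admit. Lack of a documented rate is also not the protocol's own test: it excludes pregnancy because the risk is unknown, while knowing of no documented harm. It gives hypertension its own row although inclusion 3 already reaches it. The existing safeguards are the driving and equipment warning, a study doctor reachable by telephone, daily calls in week 1 and shorter light sessions. None of them decides who is eligible.

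**Conclusion.** The concern holds. By the written rules, a patient with stable epilepsy or a remote seizure is eligible for an outpatient Wake Night of about 34 hours (cap 42) and daily bright light unless a clinician chooses to use exclusion 6. The case rests on the wording of the criteria, on the precedents in the protocol's own uploads, chiefly the triple chronotherapy pilot, and on the very low cost of correction. It does not rest on any estimate of seizure risk. On the assumed 0.5% to 2% prevalence, fewer than one such patient would be expected in the Chronotherapy arm. The change should be made; confidence is medium, because the screening protocol and consent pages could not be seen.

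**What to change.** Add one row to the exclusion table: history of seizures or epilepsy, including light-induced, ascertained by the medical history already taken. This needs one line of text and one history question. On the assumed prevalence it removes 75 × 0.005 = 0.4 to 75 × 0.02 = 1.5 patients, so probably no more than one or two of the 75 projected.

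If the investigator prefers to leave stable cases to exclusion 6, the protocol should say so, add seizure to the risk section, and note that two of the three uploaded sleep-deprivation studies excluded such patients. That is the weaker course, because it records the choice without changing who is exposed.
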